8.4.2 Exclusion criteria

- 1. Inability or unwillingness to provide written consent.
- 2. Inability or unwillingness to comply with the requirements of the protocol as determined by the investigator.
- 3. Pregnancy, breastfeeding or use of non-reliable method of contraception.
- 4. Subjects with history of chronic liver disease, chronic renal failure, heart failure, diabetes mellitus
- 5. Subjects with history of peptic ulcer disease, upper gastrointestinal bleeding, diverticulitis or ulcerative colitis.

- 6. Subjects who have recently had live or attenuated virus vaccines
- 7. Subjects with current infection (systemic fungal, active tuberculosis, cerebral malaria, viral hepatitis, HIV)
- 8. Subjects with cataracts and glaucoma
- 9. Subjects with osteoporosis
- 10. Subjects with psychiatric disorders
- 11. Subjects with complete biliary obstruction, bleeding disorders, hypertriglyceridemia (fasting triglyceride levels > 300mg/dL)
- 12. Previous history of adverse reactions to cholestyramine or other bile acid sequestrants
- 13. Previous history of adverse reactions to prednisolone or other steroid compound
- 14. Current use of cholestyramine or prednisolone or other steroid compound
- 15. Participation in another clinical trial and/or receipt of cholestyramine or prednisolone within 4 weeks prior to screening visit.
- 16. Subjects with history of bronchial asthma, bronchospasm, peripheral vascular disease or adverse reactions to propanolol
- 17. Subjects with adverse reactions to carbimazole
- 18. Hypokalemia (serum K^+ <3.5 mmol/L)
- 19. Thyroid storm defined as Burch Wartofsky Score >45

8.4.3 Subject withdrawal & drop-out

Subjects are free to withdraw from the study at any time for any reason. Subjects may also be withdrawn from the study at any time at the discretion of the investigator. The following are anticipated conditions/events that would require a subject to be withdrawn from the study:

- Adverse reactions or intolerance to study drug
- Protocol violation
- Subject requires use of unacceptable concomitant medication

- Subject not compliant with protocol procedures
- Subject develops a condition during the study that violates the inclusion/exclusion criteria
- Lost to follow-up
- Administrative problems
- Death

8.4.4 **Procedures for handling withdrawal**

Subjects who withdraw or are withdrawn from the study should:

- Have the reason(s) for their withdrawal recorded
- Be asked about the presence of any AEs and if so should be followed up by regular scheduled visits, telephone contact, correspondence or home visits until satisfactory clinical resolution of AEs is achieved.
- Be seen by an investigator and all final assessments will be performed and recorded in the OFF STUDY form.
- Be encouraged to continue coming for regular visits and assessments
- Have at least one follow-up contact (scheduled visit, telephone contact, correspondence or home visit) for safety evaluation during the 30 days following the last dose of study treatment.
- In the event of pregnancy, the subject should be monitored until conclusion of the pregnancy and the outcome of pregnancy reported.
- Have study treatment returned.

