Three treatment modalities are currently available for the management of hyperthyroidism: antithyroid drugs (ATDs), surgery, and radioactive iodine (RAI) therapy. Treatment for hyperthyroidism is aimed at restoring euthyroidism with ATDs while awaiting disease remission and resolution of autoimmunity or inducing permanent hypothyroidism with subsequent thyroxine replacement by total thyroidectomy or RAI therapy. Beta-blockers (for example propanolol and atenolol) are added to block beta-adrenergic tone for symptomatic relief of palpitations, tachycardia, tremulousness, anxiety, heat intolerance, fatigability and shortness of breath. There is currently no consensus on the "best" treatment option with various practices in different centers and countries. The choice of treatment depends on the cause of hyperthyroidism, patient's age and preference, severity of disease, glandular size, activity and severity of Graves' opthalmopathy, local practices and resources.

ATDs including methimazole, carbimazole, and propylthiouracil are effective treatments that inhibit thyroid hormone synthesis, and have clinically important immunosuppresive effects including reducing serum antithyrotropin receptor antibody concentration with time. Antithyroid drugs are an effective treatment option but these drugs take in most cases between 6 to 8 weeks to achieve euthyroidism. It has also shown to have the highest relapse rate at 52.7% compared to RAI (15%) and surgery (10%) in a recent meta analysis⁸. In addition 13% of patients on ATDs experienced adverse events with rash most common with methimazole and hepatic involvement with propylthiouracil⁸.

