Thyroid hormone is metabolized in the liver where it is conjugated to glucuronides and sulfates and excreted in the bile. Usually only 20% of circulating T₄ is excreted in the bile and released into the intestine and reabsorbed completing the enterohepatic circulation. However in the thyrotoxic states there is an increased enterohepatic circulation of thyroid hormones with an increased urinary and fecal excretion of both conjugated and FT_4^{9} . Cholestyramine is an anion exchange resin that binds T₄ in the intestine resulting in fecal excretion of T₄ thus reducing the enterohepatic circulation and absorption in hyperthyroidism. Cholestyramine has been used in cases of thyroid storm¹⁰. Cholestyramine has been studied as an adjunctive therapy to thionamides and found to be effective in reducing thyroid hormones rapidly. Solomon et al first studied the effects of cholestyramine powder (4g QID) on 15 thyrotoxic patients and shown a more rapid decline in all thyroid hormone levels in the cholestyramine group in the first 2 weeks (P<0.01)¹¹. Mercado et al similarly reported rapid decline in total and free T_4 and T_3 when cholestyramine 4g tds was added to methimazole and propanolol¹². Kaykhaei et al. demonstrated a similar efficacy with a lower dose of cholestyramine (2g BD vs 1g BD) with all patients in the cholestyramine group achieving euthyroidism in 4 weeks⁹. The main adverse effects are flatulence and constipation in 10% of cases and vomiting, diarrhea, indigestion, abdominal pain, abnormal stools, bloating, headache, and raised triglyceride levels in 1-10%, whereas muscle pain, raised liver enzymes and difficulty in swallowing are rare¹³. Patients in the trials above tolerated the drug well with only 2 reported hyperdefecation and complained of bad taste¹¹.

Steroids have been shown to be effective in controlling hyperthyroidism. It demonstrates immediate effects by inhibiting the conversion of thyroxine to triiodothyronine peripherally and also blocks the release of thyroxine from the thyroid gland. It may also have the potential to suppress the immune response

20

Confidential Date: 5th June 2017

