10 ADVERSE EVENTS

10.1 Definitions

10.1.1 Adverse event (AE)

Any untoward medical occurrence in a subject administered an investigational product and which does not necessarily have a causal relationship with treatment.

An AE includes:

- 1. A clinically significant worsening of a concomitant illness
- 2. A clinical laboratory adverse event: a clinical laboratory abnormality which is clinically significant, i.e an abnormality that suggests a disease and/or organ toxicity and is of a severity active management, Active that requires management includes active treatment or further investigations, for example change of medicine dose or more frequent follow-up due to the abnormality.

The following should be reported as AE:

Treatment of emergent symptoms which include:

- Medical conditions or signs or symptoms that was absent before starting study treatment.
- In this trial the following events must be collected and reported:
 - 1. SAEs
 - 2. AEs leading to discontinuation of study drug
 - 3. Gastrointestinal symptoms
 - a. Constipation
 - b. Bloating
 - c. Diarrhea
 - d. Abdominal pain
 - e. Vomiting
 - 4. Diabetes
 - 5. Hypokalemia
 - 6. Hypothyroid

- The following abnormal laboratory values particularly to this study will be observed
 - Fasting plasma glucose more ≥7 mmol/L or Random plasma glucose ≥ 11.1 mmol/L
 - Serum K+ <3.5mmol/L
 - TSH above upper limit of reference range and FT₄ normal or below lower limit of reference range
- Any doubtful event should be treated as an AE.

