10.4 Treatment and follow up of AE

Treatment of any AE is at the sole discretion of the investigator who should follow up subjects with AE until the event has resolved or until the condition has stabilised. Otherwise appropriate medical care should be arranged for the patient. Abnormal tests should be repeated until they return to baseline levels or an adequate explanation of the abnormality has been found.

- 1. Treatment of over-dosage significant enough to cause adverse effects
 - Study medication must be stopped immediately and subject be monitored closely for all adverse reactions. Immediate thyroid function test to be sent and reviewed.
- 2. Pregnancy
 - A female subject must be instructed to stop taking study medication and immediately inform the investigator if she becomes pregnant during the study. The investigator should counsel the subject and discuss the risks of continuing with the pregnancy and the possible effects on the foetus. Monitoring of the subject should continue until conclusion of the pregnancy. The investigator should report all pregnancies to the coordinating investigator and MREC within 24 hours of being notified of the pregnancy.
 - Pregnancy occurring in the partner of a subject participating in the study should also be reported to the investigator and sponsor. The partner should be counseled and followed as described above.
 Pregnancies will be formally reported as SAEs.
- 3. Hypokalemia
 - If mild hypokalemia (3-3.5 mmol/L), to replace with Mist Potassium Chloride and reassess K⁺ levels after 3 days. If moderate to severe hypokalemia (<3 mmol/L), to assess for symptoms and consider admission for close monitoring, ECG and oral/IV potassium replacement. To consider withdrawing treatment (especially prednisolone) if refractory to active intervention.

- 4. Diabetes
 - To reconfirm by sending a repeat FPG and 2 hour post prandial glucose. Upon confirming diagnosis of diabetes, consider starting oral hypoglycemic drugs. Consider discontinuing study treatment if severe uncontrolled hyperglycemia or hospitalisation for hyperglycemic emergencies.
- 5. Hypothyroid
 - Hypothyroid is defined as symptoms of hypothyroidism coupled with elevated TSH more 4.7mU/L and normal or low levels of Free T4 <9 pmol/L measured during intervention with study drug

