11.2 Criteria for stopping subject treatment

The investigator will discontinue a subject's taking of study treatment at any time if the subject:

1. Who no longer wishes to participate in the trial and wishes to withdraw from the study at any time

2. Experiences intolerable adverse reactions

3. Is diagnosed with any of the exclusion criteria during the intervention period

4. Develops hypothyroid during the intervention period (Hypothyroid is defined as symptoms of hypothyroidism coupled with elevated TSH > 4.7 mU/L and normal or low levels of Free T4 <9 pmol/L

In all these cases, the investigator and/or the treating physicial will if possible encourage the subject to continue with the follow up assessment and to allow the use of collected data in the analyses.

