13 STATISTICAL METHODS

13.1 Sample size and power considerations

The sample sizes estimations and analyses plan were made with the caveat that the three-treatment groups comparison is as little difference from carrying out a series of three independent trials, and to use conventional significance tests without adjustment as argued by Saville (1990)²⁰. Sample size and power considerations

Sample sizes were estimated by using PASS 11 software²¹. The estimations were based on primary objectives only.

Primary objective: To achieve 80% power to detect a 30% difference in the proportions achieving normal FT_4 between Group 3 (Carbimazole+Propanolol) and each of Group 1 (Cholestyramine + Carbimazole+ Propanolol) and Group 2 (Prednisolone+ Carbimazole+ Propanolol), 41 patients are needed in each group. The proportion achieving normal FT_4 in Group 3 was estimated to be 40%. (1) Allowing for 10% drop out rate, the sample size required is therefore 45 per arm. The test statistic used is the two-sided Z test with pooled variance.

The significance level was targeted at 0.05.

Primary objective: To achieve 80% power to detect a 30% difference in the proportions achieving normal FT_3 between Group 3 (Carbimazole+Propanolol) and each of Group 1 (Cholestyramine + Carbimazole+ Propanolol) and Group 2 (Prednisolone+ Carbimazole+ Propanolol), 41 patients are needed in each group. The proportion achieving euthyroid status in Group 3 was estimated to be 40%. (1) Allowing for 10% drop out rate, the sample size required is therefore 45 per arm. The test statistic used is the two-sided Z test with pooled variance. The significance level was targeted at 0.05.

Thus, the final sample size will be 45 per group.

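### Sections 8.4.3, 10.4 and 11.2 give conflicting rules for subjects with adverse reactions or new exclusion conditions, and 8.4.3 ends study participation where continued measurement would protect the intention-to-treat analysis

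*Combined protocol and SAP*

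**What the plan says.** Section 8.4.3 first allows withdrawal at the subject's wish or the investigator's discretion. It then gives a list under the words "The following are anticipated conditions/events that would require a subject to be withdrawn from the study". The first entry is "Adverse reactions or intolerance to study drug". Protocol violation, non-compliance with procedures, and a new condition that breaches the eligibility criteria are also listed. The action is withdrawal from the study.

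Section 11.2 covers discontinuing study treatment. Its entry for reactions is "Experiences intolerable adverse reactions". It also stops treatment for hypothyroidism and for an exclusion condition diagnosed during the intervention. The subject is then encouraged, if possible, to continue follow-up.

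Section 10.4 says "Treatment of any AE is at the sole discretion of the investigator who should follow up subjects with AE until the event has resolved" or the condition has stabilised. For low potassium and for new diabetes it describes management first, with stopping treatment only to be considered in refractory or severe cases. For significant overdose, pregnancy, hypothyroidism and thyroid storm it does stop treatment. Section 10.1.1 lists "AEs leading to discontinuation of study drug" as its own reporting class.

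Under 8.4.4, withdrawn subjects have final assessments on an off-study form, are encouraged to keep attending, and have at least one safety contact, possibly by telephone, within 30 days of the last dose. Under 8.4.5 they are not replaced. The sample size in 13.1 goes from 41 to 45 per arm, "Allowing for 10% drop out rate".

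**The concern.** The passages differ in threshold (unqualified reactions against intolerable ones) and in action (leaving the study against stopping the drug). Two sites could handle the same subject differently and both point to the protocol.

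This matters for the analysis because the triggers are unlikely to be balanced. Treatment is open label. The gastrointestinal effects belong to cholestyramine, and the glucose and potassium effects to prednisolone. Whether a subject reaches the week-2 and week-4 thyroid samples could therefore depend on the arm and on how the subject is doing. Protocol violation and non-compliance are also reasons that an intention-to-treat analysis is meant to absorb; making them grounds for mandatory study withdrawal works against the analysis planned in 13.2. The safety endpoint counts subjects with events over 6 weeks, and a subject who leaves early is observed for less time unless attendance continues.

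**Working it through.** **1. One subject, three rules.** Take a serum potassium of 3.2 mmol/L during treatment. A value below 3.5 is exclusion criterion 18 in section 8.4.2.
- 8.4.3: a new condition that breaches the eligibility criteria requires withdrawal from the study.
- 11.2, item 3: a diagnosed exclusion condition stops study treatment; follow-up is encouraged.
- 10.4: values of 3 to 3.5 are treated and rechecked after 3 days; withdrawing treatment is considered if the problem is refractory.

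New diabetes gives the same conflict, because diabetes is in exclusion criterion 4. These conflicts do not depend on how the adverse-reaction entry is read.

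**2. The plan's sample size.** Inputs from 13.1: 40% against 70%, two-sided alpha 0.05, 80% power, pooled Z test.

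n = [1.960·√(2·0.55·0.45) + 0.842·√(0.4·0.6 + 0.7·0.3)]² / 0.30² = (1.379 + 0.565)² / 0.09 ≈ 42 per arm.

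The stated 41 agrees within one. Exact enumeration of the same test gives 81.3% power at 41. For drop-out, 41/0.9 = 45.6 and 41 × 1.1 = 45.1, so the stated 45 also agrees within one. The room for loss is 45 − 41 = 4 per arm, or 4/45 = 8.9%.

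**3. Illustrative losses.** The documents give no withdrawal rate. Section 6 gives two adverse-event rates: "13% of patients on ATDs experienced adverse events" for the background drug class, and "flatulence and constipation in 10% of cases" for cholestyramine. Assume, for illustration only, that every such event leads to withdrawal and a lost outcome.
- Background alone: 45 × 0.13 = 5.9 lost per arm.
- Cholestyramine arm, events independent: 1 − 0.87 × 0.90 = 21.7%, and 45 × 0.217 = 9.8 lost. With full overlap the rate is 13%; with no overlap it is 23%.
- Prednisolone arm: no incidence is given, so nothing can be computed.

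**4. Power with those losses** (normal approximation, same test). For equal arms, power = Φ[(0.30·√n − 1.379)/0.671].
- n = 45, everyone measured: Φ(0.944) = 82.8%.
- n = 41, the planned evaluable number: 79.0%.
- n = 45 × 0.87 = 39.15 in both arms: Φ(0.743) = 77.1%.
- Unequal arms, 39.15 control and 45 × 0.783 = 35.2 cholestyramine: 74.7%.

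Even in this scenario, power falls only about 2 to 4 points below the planned position. Selective loss is the larger worry, and the documents give no basis for putting a number on it.

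**The case against.** The strongest reply is that 8.4.3 is a generic list. Its first entry pairs reactions with intolerance, it follows a sentence about investigator discretion, and it sits beside administrative problems. Read with the rest of the protocol, it need not mean every mild reaction. Section 6.1 expects constipation to be mostly mild, transient and manageable, and the separate class for events leading to discontinuation in 10.1.1 implies that other events do not lead to it. This stands. A reader might infer that the protocol orders withdrawal for any reaction however mild; the text is unqualified, but it does not say that.

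A reader might also infer that losses will exceed the 10% allowance. The documents do not support that either. The 13% has no time window and covers antithyroid drugs generally. Patients already taking these drugs may enter, and those with carbimazole reactions are excluded; both would tend to lower the rate. Section 6 reports that cholestyramine was well tolerated, and 9.1.1 says the trial dose is not considered to cause adverse reactions. The 13% to 23% range varies only the overlap of two event rates. The main uncertainty is what share of events leads to withdrawal.

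Nor is withdrawal the same as a missing outcome, since 8.4.4 and 11.2 both encourage attendance. Counting withdrawn subjects as non-responders at the rates above would reduce power to about 48%, but section 13.2 states no such rule, so that figure should not be attributed to the plan.

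The reply does not remove the potassium and diabetes conflicts, or the mandatory study withdrawal for protocol violation and non-compliance.

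**Conclusion.** The contradiction between 8.4.3, 10.4 and 11.2 is in the current text and needs no projection. Study withdrawal could be related to treatment and outcome because the trial is open label, the reactions are arm-specific, there is no replacement, and attendance after withdrawal is only encouraged. That would weaken the intention-to-treat comparison and the 6-week safety endpoint.

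The size is illustrative. Power of about 77% or 75% requires every reaction to cause withdrawal and loss of the outcome; the cholestyramine figure also assumes independent events. If only intolerable reactions count, the loss could be much smaller, and with everyone measured power is about 83%. Imbalance between arms is plausible but can be illustrated for cholestyramine only. Severity is minor to moderate.

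**What to change.** 1. In 8.4.3 and 8.4.4, separate stopping study treatment from withdrawal from the study. State that subjects who stop treatment, deviate from the protocol or are non-compliant remain in the study for the scheduled week-2, week-4 and week-6 visits and samples, unless they withdraw consent or cannot be followed, and that they are analysed in the intention-to-treat set.
2. The investigators must reconcile the adverse-reaction and exclusion-condition criteria in 8.4.3, 10.4 and 11.2 so that each situation leads to one action. Which clinical threshold is right is for them to decide and is not addressed here.

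The cost is protocol wording and a few more follow-up visits for subjects off treatment. The visits are already scheduled, and 8.4.4 and 11.2 already encourage attendance.

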8.3 Discussion of study design

All hyperthyroid subjects secondary to Graves disease identified at endocrine, endocrine surgery, general medical clinics and medical wards in Hospital Putrajaya, Hospital Queen Elizabeth II and Hospital Ampang will be screened from May 2017/ Upon approval from MREC to 31st December 2017. Potential participants will be invited to a screening visit.

Screening visit

The screening visit consists of providing information about the study, obtaining informed consent and screening assessment. The investigator will further explain the study, answer any questions and seek informed consent. All subjects will provide written informed consent to their participation in the study. The subject will then have a complete history taking, clinical examination and anthropometric measures. They will have their blood sampled, approximately 10 ml for screening tests. Subjects are eligible for the trial, if they comply with the following inclusion and exclusion criteria.

Baseline visit and Randomisation

Subjects eligible for the trial will return for baseline assessment and randomisation. They will be assigned a unique sequentially numbered study identifier according to the order in which he or she is enrolled in the trial.

The subject will then complete the baseline assessment including history taking, clinical examination, anthropometric measures, blood sampling (6 ml) and imaging (if not done previously). Following baseline assessment, subjects will be randomised into either of the 3 treatment groups. A subject will be randomly allocated to one of the three treatments per random allocation sequence that will be generated by a member of the study team.

Duration

The total trial duration is expected to be 7 weeks (1 weeks screening period, 4 weeks intervention period and 2 weeks follow up period). The intervention period for each subject will be 4 weeks. The subject will return at week 2 and week 4 of intervention for safety and compliance assessment and blood sampling (6 ml each visit) for biochemical monitoring. There will be a follow up visit 2 weeks from the end of intervention period to monitor for any adverse effects and complications and a repeat blood sampling (6ml) for biochemical monitoring.

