9.9 Assessment of safety

Safety data will be analysed for the data collected throughout intervention period and up to follow up period. The following endpoints will be collected:

- Number of subjects with adverse effects during the intervention period and follow up period (total duration 6 weeks)
 - Subjects will be asked to report about adverse reactions (specified in the protocol) at 2 weeks, 4 weeks of intervention period and 2 weeks after end of study treatment period.
 - Number of subjects with serious adverse events during intervention period and follow up period (total duration 6 weeks)
 - Subjects will be asked to report about SAE immediately during the intervention period and follow up period

Safety and tolerability assessments will consist of:

- Regular performance of physical examinations
 - 1. BP, PR, Temperature, Weight (kg)
- Regular monitoring of laboratory tests
 - FPG/ RPG, Electrolytes (Na⁺, K⁺, Urea, Creatinine), FT₄, FT₃, TSH
- Monitoring and recording all adverse reactions and serious adverse events

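### Withdrawn subjects are not required to have a safety contact at week 6, so the 6-week adverse-event count may cover a shorter window for them than for completers

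*Combined protocol and SAP*

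**What the plan says.** Safety is the only secondary objective (section 7.2). Section 9.9 defines its first endpoint as "Number of subjects with adverse effects during the intervention period and follow up period (total duration 6 weeks"), with a parallel count for serious adverse events. Subjects are asked about adverse reactions "at 2 weeks, 4 weeks of intervention period and 2 weeks after end of study treatment period". Section 8.3 gives the timetable as "1 weeks screening period, 4 weeks intervention period and 2 weeks follow up period" and states: "There will be a follow up visit 2 weeks from the end of intervention period to monitor for any adverse effects and complications". The study activities table places that visit (Visit 5) at week 6, with blood tests.

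Section 8.4.4 lists what happens on withdrawal. The subject is asked about adverse events, and any that are present are followed to resolution. The subject should also "Be seen by an investigator and all final assessments will be performed and recorded in the OFF STUDY form". Continued attendance at regular visits is encouraged. Lastly, a minimum of one further contact, which may be in person, by telephone or in writing, is due "for safety evaluation during the 30 days following the last dose of study treatment". Section 11.2 likewise encourages continued follow-up, where possible, in subjects who stop treatment.

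Section 13.2.2 compares safety proportions by a chi-square test of independence on a safety set. It has no rule for subjects observed for less than the full 6 weeks.

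**The concern.** The endpoint's clock runs for 6 weeks from the start of treatment. The clock for the one mandatory contact after withdrawal runs for 30 days from the last dose. Nothing ties the two together, so a site can follow 8.4.4 fully and never ask a withdrawn subject about new events up to week 6. A subject with no recorded event when last contacted can then be counted as event-free without having been observed for the whole window.

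This matters for the comparison of arms if withdrawal is unequal, because the arm with more early withdrawal would have more unobserved time and could look slightly safer. Unequal withdrawal is plausible: the trial is open label, the three regimens differ, and 8.4.3 makes adverse reactions or intolerance a reason for withdrawal.

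A subject who withdraws for one adverse event already counts towards the any-event endpoint. That subject can still contribute to the serious-event endpoint and to the other event types that section 10.1.1 requires to be collected. Three of those (diabetes, hypokalaemia and hypothyroidism) need a blood test, so a telephone or postal contact would not detect them.

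**Working it through.** **The plan's own window.** 4 weeks of intervention + 2 weeks of follow-up = 6 weeks = 42 days (sections 8.3 and 9.9). This reproduces the stated duration. A completer takes the last dose on about day 28 and is seen on day 42, 14 days later.

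**Range of the mandatory contact.** For a last dose on day t, the contact required by 8.4.4 may fall anywhere from day t to day t + 30. The uncovered part of the 42 days is at most 42 − t and at least max(0, 42 − (t + 30)).

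| Last dose (day) | Permitted contact (days) | Days of the 42 not covered |
|---|---|---|
| 1 | 1 to 31 | 11 to 41 |
| 7 | 7 to 37 | 5 to 35 |
| 12 | 12 to 42 | 0 to 30 |
| 14 | 14 to 44 | 0 to 28 |
| 21 | 21 to 51 | 0 to 21 |

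Since t + 30 < 42 whenever t < 12, a last dose before day 12 leaves a gap even with the latest permitted contact, unless the subject also keeps attending visits. From day 12 on, the contact can reach day 42 but need not.

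**Size.** The documents give no adverse-event risk by arm and no timing of withdrawal, so these inputs are assumptions:
- constant hazard over 42 days;
- 6-week risk p of 10%, 20%, 30% or 40%;
- withdrawn subjects observed for 14 days, with no later contact.

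The withdrawn fraction is set at the 10% drop-out rate in section 13.1, which is 0.10 × 45 = 4.5 subjects per arm.

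Chance of a recorded event by day 14: q = 1 − (1 − p)^(14/42).
Recorded proportion in the arm: 0.9 × p + 0.1 × q.
Loss: 0.1 × (p − q).

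| p | q | Recorded | Loss (points) | Loss (subjects of 45) |
|---|---|---|---|---|
| 10% | 3.5% | 9.3% | 0.7 | 0.3 |
| 20% | 7.2% | 18.7% | 1.3 | 0.6 |
| 30% | 11.2% | 28.1% | 1.9 | 0.8 |
| 40% | 15.7% | 37.6% | 2.4 | 1.1 |

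The loss is therefore about 1 to 2.5 points in an arm (0.7 to 2.4 before rounding). It is proportional to the fraction withdrawn. With equal risk and equal withdrawal in two arms it cancels from the difference. With a 10-point imbalance in withdrawal, the spurious difference is the figure in the table.

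**Sensitivity.** If half of the withdrawn subjects already have a recorded event, the loss halves, to about 0.3 to 1.2 points. At the unfavourable end, if all are observed for only 8 days and p is 40%, then q = 1 − 0.6^(8/42) = 9.3% and the loss is 0.1 × (40 − 9.3) = 3.1 points.

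**The case against.** The strongest reply is that 8.4.4 asks for a good deal more than one contact. There is an adverse-event enquiry at withdrawal, an investigator visit with final assessments, follow-up of known events to resolution, and encouragement to keep attending, which would include Visit 5. Section 9.9 also asks subjects to report serious events immediately throughout intervention and follow-up. So a reader who infers that withdrawn subjects receive a single contact and nothing else goes further than the text. This stands, and it means that many withdrawn subjects may in fact be seen at week 6. It does not close the gap, because those duties concern the moment of withdrawal or events already known. None requires an enquiry about new events up to week 6.

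A reader might also infer that a contact as late as day 58 (28 + 30) would add events from days 43 to 58 for withdrawn subjects alone. The documents do not support that. The endpoint is limited to 6 weeks and section 10.2 records start and end dates, so an event starting after day 42 falls outside the count whenever it is learned of.

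Nor can one say that every withdrawn subject stays in the safety denominator, because the safety set is named but not defined. The plan does not forecast different withdrawal by arm either; section 13.1 uses one 10% rate throughout.

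Finally, the effect is small beside sampling error. With 45 per arm and 40% in each, the 95% half-width for a difference is 1.96 × √(2 × 0.4 × 0.6 / 45) = 20 points. That is correct, and it limits the weight of the point. It does not argue against a correction this cheap.

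**Conclusion.** The point holds in a limited form. No week-6 safety assessment is required for withdrawn subjects, and the analysis makes no allowance for unequal observation. The 6-week count may therefore cover a shorter window for them. A shortfall is certain only for a subject whose last dose is before day 12 and who does not continue visits; with a later last dose it depends on when the contact is made.

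The likely under-count is about 1 to 2.5 points in an arm, on the stated assumptions of constant hazard, 6-week risk of 10% to 40%, and 10% withdrawn and observed for 14 days. It is less if withdrawn subjects already have an event or keep attending, and it distorts the comparison mainly when withdrawal is unbalanced. The stronger inference, that the safety comparison is seriously biased, is not supported. The 3.1-point figure needs every withdrawn subject to be observed for only 8 days, with no earlier event over-represented among them, at the top of the assumed risk range. This is a cheap improvement of modest size to the only secondary objective.

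**What to change.** In 8.4.4, keep the 30-day contact and add that withdrawn subjects who can be reached and who agree have a safety contact at week 6 from randomisation, the Visit 5 time point. A telephone call is the minimum. The Visit 5 visit with its blood tests should be offered, because diabetes, hypokalaemia and hypothyroidism cannot be picked up by telephone.

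The cost is one sentence in the protocol and about one extra contact per withdrawn subject: at the planned 10% drop-out, 0.10 × 135 = 13.5, so about 14 contacts in the whole trial. For some subjects the week-6 contact will fall within the 30 days and serve both purposes. It cannot cover subjects lost to follow-up, so some unequal observation will remain.
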